4.5 Radiology Assessments (if applicable)

Not applicable

4.6 End of Study Definition

The end of the study is defined as 3 months after the completion of the final data capture (i.e. final data collection with final participant). The CI will notify the REC that the trial has ended and a summary of the trial report will be provided within 12 months of the end of trial.

5. Laboratories (if Applicable)

Not applicable

6. Assessment of Safety

The collection and reporting of adverse events (AEs) and Serious Adverse Events (SAEs) will be in accordance with Good Clinical Practice and the Research Governance Framework 2005. Definitions will be as defined in the Guys and St Thomas Foundation NHS Trust Standard Operating Procedures for the Identifying, Recording and Reporting Adverse Events.

Safety will be assessed continuously throughout the trial. There are no Investigational Medicinal Products being used as part of the MOSAIC study.

There may be a small increased risk of a temporary increase in pain on walking during the assessment and completion of MOSAIC as it is a requirement of the walking exercise that pain is

induced within 3-5 minutes of commencing walking. Physiotherapists are trained to identify and address any untoward increases in pain. No other risks are expected to arise from taking part in the trial. It is therefore, reasonable to collect only targeted treatment-related AEs.

Adverse events (AEs)) will be recorded from date of consent to the 6 month outcome assessment.

All AEs will reported to the CI.

Physiotherapists treating participants randomized to MOSAIC will be trained to identify and report AEs in a standard format.

All participants will report AEs to the RA at follow up assessments (in response to one open ended question "Have you had any problems since your last assessment /questionnaires?"). These will be reported by the RA in a standard format.

Serious Adverse Events

Investigators (or their delegates) should contact the CI within 24 hours of becoming aware of a suspected SAE.

Participants will be contacted by the PI and the PI will decide whether a SAE has occurred and act in accordance to Safety Reporting in Non-CTIMP Research Stand operating procedures (Appendix 1). The PI will be also asked to provide a categorisation of seriousness and causality. The form should be sent to the CI and a copy kept in the site file.

Investigators should also report SAEs to their own Trust in accordance with local practice.

The Trial Steering Committee/Data and Ethics Monitoring Committee will monitor all AEs.

6.1 Ethics Reporting

Annual progress reports will be submitted to the Research Ethics Committee.

7. Trial Steering Committee (if applicable)

The Trial Management Group (TMG) comprising Chief Investigator, RA, trial statistician and other research team members, as required, will meet weekly to monitor the day to day running of the trial. The independently chaired combined Trial Steering Committee /Data Monitoring and Ethics Committee will meet every 6 months and oversee the trial procedures including monitoring recruitment, data completeness and patient safety (i.e., AEs). The TSC/DMEC will include the research team, a statistician, an independent chair and other independent members including at least one Patient Advisor.

8. Ethics & Regulatory Approvals

The study will be submitted to an NHS REC and the governance review (following REC approval) will be undertaken by local Research and Development departments.

9. Data Handling Confidentiality Personal data, including address and telephone number, will be held for all participants for the duration of the study in a secured database maintained confidentially and separately from patient-reported research outcomes.

Participants will be allocated a unique participation number which will be used to anonymously label all data from questionnaires and assessments.

Audio recording may be used during the qualitative interviews and questionnaire feedback sessions. Recordings will be transcribed for analysis and audio files will be destroyed once transcription is complete. Any transcription service will sign a privacy agreement.

Direct quotations may be used from the transcriptions but all identifiable information will be removed (e.g, names of people or hospitals etc) prior to publication.

For participants assigned to the intervention group, all treatment sessions will be audio recorded and a proportion analysed by the research team against standardised checklists to assess therapists' fidelity to the protocol (see Section 4.5E).

All data will be password protected and encrypted and stored on secure servers at King's College London. Data stored on external devices such as laptops and external hard drives will be encrypted and password protected. Only anonymised data will be stored on external devices. Personal identifiable information such as names and address will be stored as hard copy in a locked filing cabinet or in a password protected, encrypted file on the King's College London secure server.

In line with the Data Protection Act (1998), the minimum identifiable data will be sought and the identification list of participant details will be stored in a locked cabinet and on the desktop university password protected computer inside the locked office of the CI. Paper copies (for example signed consent forms and any questionnaires completed on paper) will be stored in a locked filing cabinet at King's College London and available only to members of the research team. Electronic files will be encrypted and password protected and stored on a secure server within King's College London and again, will only be accessible by members of the research team.

Case Report Form

A case report form (CRF) will be completed for each participant. The following details will be included in the case report form for each participant: eligibility/exclusion criteria checklist, date of consent, baseline assessments, date of intervention commencement, AEs, withdrawal from study, follow up of outcomes, SAE form. The form will be completed by the Principal Investigator (or delegates, as recorded on the MOSAIC trial delegation log) i.e. research nurse, the trial physiotherapist and the RA.

Record Retention and Archiving

All records will be anonymised and kept for 5 years after the end of the trial.

Compliance

The CI will ensure that the trial is conducted in compliance with the principles of the Declaration of Helsinki (1996), and in accordance with all applicable regulatory requirements

including but not limited to the Research Governance Framework, Trust and Research Office policies and procedures and any subsequent amendments.

10. Finance and Publication Policy

Name and address of funder Name: Dunhill Medical Trust Address: [name]; [contact] [contact] Email: [contact]

Amount of funding awarded: £299,495

The trial will be registered on the ISRCTN trial registry as well as the UKCRN Research Portfolio.

Dissemination plan;

Service users, participants and funding body will be provided with a summary of our findings. Patient Advisors will present the findings and share their own related experiences, supporting the impact of this research to practitioners, researchers and patients. The study protocol will be published in an open access journal (e.g. Trials/BMJ Open) and results will be published in relevant clinical and academic journals (e.g., European Journal of Vascular and Endovascular Surgery, Physiotherapy, British Journal of Health Psychology). Abstracts will be presented at academic (e.g. The Vascular Society of Great Britain and Ireland, Physiotherapy UK, UK Society of Behavioural Medicine) and clinical forums (e.g. King's Health Partners). We will publish study updates and results via social media (e.g. twitter) and the King's Health Partners and Division of Health and Social Care Research websites.

	Who	When	How	To Whom
SAE	Chief Investigator	-Report to Sponsor within 24 hours of learning of the event -Report to the MREC within 15 days of learning of the event	SAE Report form for Non- CTIMPs, available from NRES website.	Sponsor and MREC
Urgent Safety Measures	Chief Investigator	Contact the Sponsor and MREC Immediately Within 3 days	By phone	Main REC and Sponsor

Appendix 1 – Information with regards to Safety Reporting in Non-CTIMP Research

			Substantial amendment form giving notice in writing setting out the reasons for the urgent safety measures and the plan for future action.	Main REC with a copy also sent to the sponsor. The MREC will acknowledge this within 30 days of receipt.
Progress Reports	Chief Investigator	Annually (starting 12 months after the date of favourable opinion)	Annual Progress Report Form (non-CTIMPs) available from the NRES website	Main REC
Declaration of the conclusion or early termination of the study	Chief Investigator	Within 90 days (conclusion) Within 15 days (early termination) The end of study should be defined in the protocol	End of Study Declaration form available from the NRES website	Main REC with a copy to be sent to the sponsor
Summary of final Report	Chief Investigator	Within one year of conclusion of the Research	No Standard Format However, the following Information should be included:- Where the study has met its objectives, the main findings and arrangements for publication or dissemination including feedback to participants	Main REC with a copy to be sent to the sponsor

References

- Ajzen I. (1985) From intentions to actions: a theory of planned behavior. In: Kuhl JE and Beckmann Jr E (Eds) Action control : from cognition to behavior. Berlin: Springer, 11-39.
- Ajzen I. (1991) The theory of planned behavior. *Organ Behav Hum Decis Process* 50(2): 179-211. Ajzen, I., (2013) *Theory of Planned Behaviour Questionnaire*, in *Measurement Instrument*

Database for the Social Science. www.midss.ie.

- American Thoracic Society, *ATS Statement: Guidelines for the Six-Minute Walk Test.* American Journal of Respiratory Critical Care Medicine, 2002. **166**: p. 111-117.
- Booth, M.L., *Assessment of Physical Activity: An International Perspective.* Research Quarterly for Exercise and Sport, 2000. **71**(2): p. s114-20.

- Criqui, M.H., J.O. Denenberg, C.E. Bird, A. Fronek, M.R. Klauber and R.D. Langer, *The correlation* between symptoms and non-invasive test results in patients referred for peripheral arterial disease testing. Vascular medicine (London, England), 1995. **1**(1): p. 65-71.

10.1 General Methodology						
	10.2	L	oss to follow up and Missing Data12			

1	0.3	Interim Analysis and Data Monitoring	.13		
1	0.4	Multiple Comparison/multiplicity adjustments			
1	0.5	Sociodemographic and Clinical Descriptive Characteristics	.13		
	10.5.1	L Exploratory analyses	.13		
1	0.6	Primary Analysis	.13		
11	Secon	idary analysis	.13		
	11.1.1	L Calculation of MCID	.13		
	11.1.2	2 Sensitivity analysis	.14		
	11.1.3				
	11.1.4	1 Mediation analysis	.14		
	11.1.5	5 Subgroup analyses			
12	Baseli	seline data analysis			
13	Software1				
14	Bibliography15				

1 Abbreviations

6MWD - 6 Minute Walking Distance 6MWT - 6 Minute Walking Test **ABPI - Ankle Brachial Pressure Index** AEs - Adverse Events **ANOVA - Analysis of Variance** BMI - Body Mass Index Brief IPQ - Brief Illness Perception Questionnaire **CI** - Chief Investigator CTIMP - Clinical Trial of an Investigational Medicinal Product CTU - Clinical Trials Unit EARS - Exercise Adherence Rating Scale IC - Intermittent Claudication ICC - Intraclass Correlation Coefficient IPAQ - International Physical Activity Questionnaire IQR – Interguartile Range ITT - Intention to Treat MCID - Minimal Clinically Important Difference MOSAIC - MOtivating Structured walking Activity in Intermittent Claudication NHS - National Health Service NEADL - Nottingham Extended Activities of Daily Living PAD - Peripheral Arterial Disease PI - Principal Investigator PP - Per Protocol

QoL - Quality of Life RA - Research Associate REC - Research Ethics Committee ROC - Receiver Operating Characteristic SAEs - Serious Adverse Events SD - Standard Deviation SDCQ - San Diego Claudication Questionnaire SEM - Standard Error of Measurement SR-MWD - Self Reported-Maximum Walking Distance TPBQ - Theory of Planned Behaviour Questionnaire TSC/DMEC - Trial Steering Committee/Data Monitoring and Ethics Committee VasculQoL-6 - Vascular Quality of Life Questionnaire-6 WELCH - Walking Estimated Limitation Calculated by History

2 Preface

This document is to provide a more technical and detailed description of the principal features of the analysis stated in the protocol, and to include detailed procedures for executing the statistical analysis of the primary and secondary variables and other data.

The following document was written based on the MOSAIC protocol version 5.

3 Study Design

Motivating Structured walking Activity in Intermittent Claudication (MOSAIC) is a phase II, multi-centre, parallel group, two-arm, randomised, controlled superiority trial with a 1:1 allocation ratio, stratified by recruitment site. Participants will be randomised to receive either usual National Health Service (NHS) care or MOSAIC in addition to usual NHS care.

MOSAIC comprises 2 x 60-minute individual face-to-face consultations (weeks 1 & 2) and 2 x 20-minute follow-up telephone calls (weeks 6 & 12) delivered at a convenient time and location of participant's choice (local NHS Trust or participant's home). All sessions are delivered by a trained Band 6/7 physiotherapist. A checklist outlining the components for each session will be provided to each physiotherapist. All participants randomised to receive MOSAIC will be provided with a pedometer and a patient manual which will include information on intermittent claudication (IC), risk factors, walking guidelines, goal setting, problem solving and action planning worksheets and a walking diary.

Usual care comparison: Participants randomised to the comparison group will continue to receive usual NHS care for IC which typically consists of an initial assessment, drug therapy and simple advice to walk provided by a vascular specialist and delivered in the vascular outpatient clinic. The type and duration of usual NHS care treatment received by both groups will be recorded. The opportunity for between group contamination is low as usual NHS care is not delivered by physiotherapists.

3.1 Trial Flowchart

4 Method of allocation to groups

Once baseline assessments are complete, the individuals will be randomised to one of the treatment arms. Randomisation will be done in a 1:1 ratio. Randomisation is at the participant level and is performed using an online randomisation system set up by the King's College London Clinical Trials Unit (CTU). Randomisation is stratified by recruitment site with

variable block sizes to ensure that equal numbers of patients are allocated to the two arms within each site. The procedure is as follows: On receipt of the baseline questionnaire, the Trial Co-ordinator electronically submits details of each participant to the CTU. This includes: participant ID number, site, initials and date of birth. The system immediately notifies the chief investigator (CI) and assigned members of the research and clinical teams, as well as recording the randomisation outcome. The Trial Co-ordinator does not receive the randomisation outcome.

4.1 Duration of the treatment period

The treatment period is 12 weeks (3 months).

4.2 Frequency and duration of follow-up

Participants will complete follow up measures at 3 months for the primary outcome. Participants will complete follow up measures at 3 and 6 months for the secondary outcomes.

4.3 Visit windows

The MOSAIC intervention visit windows are weeks: 1, 2, 6 and 12.

Both groups are assessed at week 0 (baseline), week 12 (3 months) and week 24 (6 months) follow up.

5 Data collection

5.1 Inclusion criteria

Participants will be eligible for the trial if they meet the following inclusion criteria:

- ≥50 years of age;
- Established peripheral arterial disease (PAD) (determined by either (i) Ankle Brachial Pressure Index ≤0.90; (ii) radiographic evidence or (iii) clinician reported diagnosis) and IC (symptoms reported on the San Diego Claudication Questionnaire (SDCQ)).
- Able and willing to participate in MOSAIC.
- Able and willing to provide informed consent.
- 5.2 Exclusion Criteria
 - Unstable IC (self-reported change in symptoms during previous 3 months).
 - Walking >90 minutes/week (reported on Brief International Physical Activity Questionnaire (IPAQ)).
 - Contraindications to walking exercise (e.g. unstable angina) confirmed by the direct care team.
 - Have completed any prescribed supervised exercise sessions in the previous 6 months or been offered prescribed supervised exercise sessions in the next 6 months.

5.3 Measures

5.3.1 Baseline

Measures collected by self-report include:

- Age
- Gender
- Ethnicity
- Marital status
- Smoking history
- Co-morbidities
- Duration of PAD diagnosis and IC symptoms
- Prescribed medication for IC
- History of revascularisation
- Walking advice

The following measures will be obtained by the outcome assessor:

- Standard measures of body mass index (BMI)
- Ankle Brachial Pressure Index (ABPI)
- Current symptoms described by the SDCQ

5.3.2 Primary

6 Minute Walking Distance (6MWD in metres) is measured during a self-paced, standardised 6 Minute Walking Test (6MWT) conducted around a level, 100-foot circuit [1, 2]. During the 6MWT, maximal walking ability (time (seconds) walked before resting) and pain free walking ability (time (seconds) walked before reported pain onset) will be measured. Pain intensity will also be measured before and after the walking test using the Claudication Pain Scale. The walk test is completed twice, with the results from the best test (i.e. the highest 6MWD) used for analysis; using the highest 6MWD is based on the American Thoracic Society guidelines for the 6MWT [2].

5.3.3 Secondary

The following secondary measures will be collected at baseline, 3 months and 6 months:

- Self-reported Maximum Walking Distance (SR-MWD)
- Walking Estimated-Limitation Calculated by History (WELCH) questionnaire
- Nottingham Extended Activities of Daily Living (NEADL) questionnaire
- Vascular Quality of Life Questionnaire-6 (VasculQoL-6)
- The Brief Illness Perception Questionnaire (Brief IPQ)
- The Theory of Planned Behaviour Questionnaire (TPBQ)
- The action planning and action control scale
- Brief International Physical Activity Questionnaire (IPAQ)

5.3.4 Additional post randomisation measures

These measures will be assessed at 3 months and 6 months:

• Exercise Adherence Rating Scale (EARS)

5.4 Adverse events

Safety will be assessed continuously throughout the trial. There are no investigational medicinal products being used as part of the MOSAIC trial.

There may be a small increased risk of a temporary increase in pain on walking during the assessment and completion of MOSAIC as it is a requirement of the walking exercise that pain is induced within 3 to 5 minutes of commencing walking. Physiotherapists are trained to identify and address any untoward increases in pain. No other risks are expected to arise from taking part in the trial. It is therefore, reasonable to collect only targeted treatment-related AEs (AEs).

The collection and reporting of AEs and Serious Adverse Events (SAEs) will be in accordance with Good Clinical Practice and the Research Governance Framework 2005. Definitions will be as defined in the Guys and St Thomas Foundation NHS Trust Standard Operating Procedures for the Identifying, Recording and Reporting Adverse Events.

AEs will be recorded from date of consent to the 6-month outcome assessment. All AEs will be reported to the CI. Physiotherapists treating participants randomised to MOSAIC will be trained to identify and report AEs in a standard format.

All participants will report AEs to the Research Associate (RA) at 3 and 6 month follow up assessments (in response to one open ended question "Have you had any problems since your last assessment /questionnaires?" These will be reported by the RA in a standard format.

The number of AEs will be reported with proportions and 95% confidence intervals for differences between the groups, where appropriate.

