3.3 Criteria for Premature Withdrawal

Participants will be free to withdraw their participation in the trial at any time. We do not anticipate that there will be any requirement for a premature withdrawal.

All adverse events will be reported to the Chief Investigator who will be responsible for reporting to the Trial Steering Committee/ Data Monitoring and Ethics Committee, study sponsors, Research and Development departments and Research Ethics Committee. (Please see section 6, Appendix 1)

4. Study procedures Informed Consent Procedures

Informed consent will be sought from all participants.

It is the responsibility of the Investigator to obtain written informed consent for each participant prior to performing any trial related procedures. However, this task may be delegated to suitably trained individuals e.g. Research Nurses, Research Associate (RA) if local practice allows and this responsibility has been delegated by the Principal Investigator as captured on the MOSAIC Trial site signature and delegation log.

Once a potential participant has decided they want to take part in the study, they will be asked to sign a consent form. Given the low risk nature of the trial and the limited mobility of some of the potential participants, patients can consent on the day they are informed of the trial, or if they prefer, they can take the participant information sheet and invitation letter home and decide to join the trial at a later date. If the patient would like to be contacted by the RA, they will be asked to provide permission to be contacted to speak on the telephone about the study and/or arrange an appointment to attend King's College London (or their local hospital, if available). At this appointment the RA, who has completed training in Good Clinical Practice and the collection of informed consent, will review the information sheet, answer any further questions and the patient can sign an informed consent form.

The investigator or delegates (as per the MOSAIC Trial site signature and delegation log) will then sign and date the form. A copy of the informed consent form will be given to the participant, a copy will be filed in the medical notes, and the original placed in the Investigator Site File.

Whilst the initial trial procedures may vary across recruitment sites, it is likely that research nurses from the Comprehensive Research Networks (CRN) will assist in the screening and consent processes.

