4.2 Randomization Procedures

Following informed consent and completion of the baseline assessment, the participant can be randomised into the trial. Participants will be randomised at the level of the individual, stratified within recruitment site, to receive either MOSAIC plus usual NHS care or usual NHS care alone in a ratio of 1:1. The King's College London Clinical Trials Unit will provide randomisation. The system is online and can be accessed 24 hours a day. The RA will log in, enter key information about the participant, and the randomisation allocation occurs instantly. Confirmation emails will be generated automatically and sent to the CI (and delegated members of the research team) and trial physiotherapists delivering MOSAIC. The RA, who is the outcome assessor, will be blind to group allocation. Once the participant is randomised they will be given a unique trial identifying number.

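### The plan both restricts AE collection to targeted treatment-related events and requires all AEs, so the events in the planned between-arm AE difference are undefined, and following the restriction would push that difference against MOSAIC

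*SAP*

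**What the plan says.** The restricting sentence appears in Protocol section 6 and again in SAP 5.4. After naming a temporary rise in walking pain as the one foreseen risk, the Protocol says "No other risks are expected to arise from taking part in the trial", and both documents conclude that it is "reasonable to collect only targeted treatment-related AEs".

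The unrestricted statements stand beside it:

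- SAP 5.4: "All AEs will be reported to the CI", and "AEs will be recorded from date of consent to the 6-month outcome assessment". Protocol section 6 has both rules.
- Protocol 3.3: "All adverse events will be reported to the Chief Investigator who will be responsible for reporting".
- SAP 5.4: "All participants will report AEs to the Research Associate (RA) at 3 and 6 month follow up assessments", in reply to one open question, "Have you had any problems since your last assessment /questionnaires".
- Protocol section 6 and SAP 5.4.1: the combined steering and monitoring committee monitors all AEs.

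On roles, Protocol 4.2 says "The RA, who is the outcome assessor, will be blind to group allocation". The RA writes up the participants' answers. Physiotherapists treating MOSAIC participants are also trained to identify and report AEs; usual care has no counterpart. Causality is mentioned only for SAEs, where the PI categorises it.

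SAP 5.4 and SAP 12 plan AE proportions with 95% CIs for the difference between groups, where appropriate. The safety set in SAP 9.3 is all participants.

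**The concern.** A site or analyst who follows the restricting sentence and one who follows the other statements will build different AE datasets from the same participants. The SAP does not say which dataset feeds the between-arm difference.

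The choice affects the result. Only the MOSAIC arm has a trial intervention to which an event can be attributed, so a relatedness condition at entry will tend to admit more events there than in usual care, even when the underlying problems are equally common. Non-serious problems that nobody connects with the intervention are lost before the arms are compared, although randomisation would have allowed an unexpected excess to be seen. Protocol 4.4 part C also asks the process evaluation to look at unexpected consequences, AEs included. A set limited to expected, related events cannot serve that aim.

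**Working it through.** **Setting the rules side by side**

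| Question | Restricting sentence | Other statements |
|---|---|---|
| Which events? | Targeted ones only; no list in these documents | All AEs (Protocol 3.3 and 6; SAP 5.4 and 5.4.1) |
| Related or not? | Related only; no criteria given | No condition |
| From when? | Only once there is a treatment to relate to | From consent, which precedes randomisation (Protocol 4.2; SAP 4) |
| How elicited? | Not stated | Open question to all participants at 3 and 6 months |
| Who judges relatedness of non-serious AEs? | Nobody named | Nobody named; the PI judges causality for SAEs only |
| What enters the difference and CI? | Not stated | Not stated |

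No reading satisfies both columns, and the last row shows that the SAP does not settle which one governs the analysis.

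**Illustration of direction and possible size**

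The plan has no AE rate to reproduce. The only document inputs are 192 participants and 1:1 allocation, so 192/2 = 96 per arm. Everything else here is an assumption: no true harm, and 20% to 40% of participants having some problem in each arm. Intervals are Wald: d ± 1.96 × √[p1(1−p1)/96 + p0(1−p0)/96].

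1. *All problems counted, one common source.* p1 = p0 = b, so d = 0. For b = 0.20 the half-width is 1.96 × √(2 × 0.20 × 0.80/96) = 0.113. For b = 0.40 it is 1.96 × √(2 × 0.40 × 0.60/96) = 0.139.

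2. *Related events only.* Let f1 and f0 be the fractions of problems labelled related in MOSAIC and in usual care. Then d = b × f1 − b × f0. Taking f0 = 0 as the limiting case:

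| b | f1 = 0.10 | f1 = 0.25 | f1 = 0.50 |
|---|---|---|---|
| 0.20 | +2 (−0.8 to 4.8) | +5 (0.6 to 9.4) | +10 (4 to 16) |
| 0.40 | +4 (0.1 to 7.9) | +10 (4 to 16) | +20 (12 to 28) |

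Entries are percentage points with 95% CI. The CI excludes 0 in five of six settings, although Wald intervals are too narrow when one arm has no events. If f0 is above 0 the shift shrinks: b = 0.40, f1 = 0.25, f0 = 0.10 gives 10 − 4 = +6 points. It stays positive while f1 exceeds f0.

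3. *All AEs, with physiotherapist reports added in MOSAIC only.* Let the RA's question capture a fraction s of those with a problem (true risk T in both arms), and let physiotherapists independently capture a fraction q. Then d = T[1 − (1−s)(1−q)] − Ts = T(1−s)q. Over T = 0.20 to 0.40, s = 0.60 to 0.80 and q = 0.25 to 0.50, the smallest value is 0.20 × 0.20 × 0.25 = +1 point and the largest is 0.40 × 0.40 × 0.50 = +8 points. Each of these CIs includes 0, but the shift is systematic.

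The same underlying events thus give an expected difference of 0 in step 1, +2 to +20 in step 2 and +1 to +8 in step 3.

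**The case against.** The best defence is that the restricting sentence is only a rationale and the operative rules are the unrestricted ones. Every participant is asked the open question, the answers are written up, the Chief Investigator receives all AEs and the committee monitors them. If all AEs are counted, the difference has a clear meaning. That is a fair account of what may happen in practice. But neither document makes the restricting sentence subordinate, and the SAP never says that all AEs are counted. Reading each later mention of AEs as the restricted set does not reconcile the text either: Protocol 3.3 refers to all adverse events without qualification, and the question is open.

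A reader might also infer several stronger things that the documents do not support:

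- *That usual care is zero by definition.* The named pain risk also arises at the walking assessments, which both arms undergo. The f0 = 0 case above is a limit, not a consequence of the plan.
- *That the blinded RA is asked to judge relatedness and cannot.* The RA only records and reports. The Chief Investigator is told the allocation (SAP 4) and receives all AEs. The gap is that nobody is assigned the judgement for non-serious AEs.
- *That the bias could run either way, with physiotherapists filtering and the RA not.* MOSAIC participants answer the same RA question, so usual care would look worse only if their answers were discarded. Nothing says so.
- *That serious cardiac events or serious falls would be missed.* Suspected SAEs go to the Chief Investigator within 24 hours with no relatedness condition, and SAP 5.4.1 gives SAEs their own between-group comparison.
- *That the exclusion of unstable angina contradicts the low-risk premise.* Excluding people with contraindications is consistent with expecting little risk in those enrolled.
- *That no list of targeted events exists anywhere.* Definitions are deferred to a Trust procedure that is not among these documents, and it may define some terms. It would not remove the conflict between the two scope statements.

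**Conclusion.** The point holds as an internal contradiction about which AEs are collected, together with an undefined set of events in a planned between-arm difference. If the restriction is followed, non-serious events not thought related drop out before comparison and the difference moves against MOSAIC. Physiotherapist reporting in that arm alone moves it the same way, and would do so even if all AEs were counted.

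The true size cannot be computed, because the documents give no AE rate. The illustrative shifts rest on assumed rates of problems, labelling and capture; the direction rests only on MOSAIC being the arm with a trial intervention and an extra reporting source. The primary 6MWD analysis and the suspected-SAE route are not affected. The change should be made, because the AE comparison cannot be interpreted as written.

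**What to change.** 1. Delete the restricting sentence in Protocol section 6 and SAP 5.4, and state that every problem reported in either arm is recorded, whatever its presumed cause.
2. In SAP 5.4 and SAP 12, define the between-arm AE difference and its 95% CI on all-cause events from the RA's common question at 3 and 6 months.
3. Show physiotherapist-reported events separately, outside that difference. Deleting the sentence alone would leave two reporting sources in one arm and one in the other.
4. Name a role other than the blinded RA to assign relatedness of non-serious AEs after recording. Show the result as a descriptive column; it must not decide which events enter the comparison.

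The cost is wording in two documents and a few more AE forms, many of them for minor or unrelated problems. The open question already collects the information. The SAE provisions need no change on this account.
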